## Objectives and Hypotheses

### General Objective

To compare the distribution of pulmonary ventilation by Electrical Impedance Tomography (EIT) during the use of the Modified Pachon's incentive (Incentivo Modificado de Pachon (IMP) by the name in Spanish) and a Branded respiratory incentive “Triflo II®”, in healthy volunteers from the City of Cali (Colombia).

### Specific Objectives:

- Describe the sociodemographic, anthropometric, clinical and spirometric characteristics of the study participants.
- Determine the global and regional pulmonary impedance through the EIT during the use of the IMP.
- Determine the global and regional pulmonary impedance through the EIT during the use of the Triflo II®.

### Hypothesis

#### Null Hypothesis:

The distribution of pulmonary ventilation, measured by EIT, between the IMP and the Triflo II® in the healthy volunteers of the City of Cali, is NOT similar.

#### Alternate Hypothesis

YES, the distribution of pulmonary ventilation, measured by EIT, between the IMP and the branded flow incentive “Triflo II®” in healthy volunteers of the City of Cali, is similar.

## Methods

### Study Design

Crossover clinical trial, in which the measurement of the distribution of pulmonary ventilation by means of EIT will be evaluated, during the use of a Branded flow respiratory incentive “Triflo II®” and the IMP, in a sample of healthy volunteers from the city of Santiago de Cali. Both incentives will be used on all participants, and the order of assignment will be randomized.

### Target Population

Healthy adults between 18 - 65 years. The population was calculated taking into account that the greatest use of the incentive reported in the literature is related to chest trauma. According to Botache W, et al In Cali, chest trauma occurs mostly in the population within these age ranges and among the most injured organs are the lungs; using as part of the treatment the respiratory incentive

### Population Sample

Sample size of 18 subjects (9 men, 9 women) healthy volunteers from the Municipality of Santiago de Cali. The type of sampling will be non-probabilistic for convenience.

### Distribution Age Ranges

Age Range	Men	Wome
18 – 34	3	3
35 – 50	3	3
51 – 65	3	3

### Selection criteria

#### Inclusion criteria:

- People aged between 18-65 years

- People with clinical stability, defined as the absence of any acute illness during the previous 6 weeks and a Charlson index score of 0-1 (12% mortality/year- no comorbidity)
- People with a body mass index (BMI) of 18.5 – 35 Kg/m^2(52,53)
- People without mental or cognitive alterations
- People who accept informed consent

**Exclusion criteria:**

- People with pacemakers, cardioverters or cardio defibrillators.
- People with metal implants
- People with any condition in which the registration in the CT scanner signal is low.
- Women in pregnancy
- Participants with injuries, skin changes or presence of devices that prevent the placement of the electrode belt around the chest.
- People with a high level of physical activity according to the IPAQ questionnaire short version
- People whose spirometry registers obstruction or restriction
- People who do not understand the verbal command of the incentive technique

**Abandonment criteria**

- Request by the subject to be excluded from the protocol expressed verbally or in writing

## Ethical aspects

According to the Declaration of Helsinki, the ethical principles for medical research on human beings, including the investigation of human material and identifiable information, and according to the scientific and technical standards established in Resolution 8439 of 1993, for health research, and according to its Article 11. This research is classified with a minimum risk due to the fact that in this project common procedures will be carried out, such as the anthropometric measurement of the height and weight of the subject in a healthy volunteers, deep and forced breathing maneuvers will be requested that are not expected to have adverse events since the patients are healthy and these procedures do not represent physical or psychological risks. however, for the study, the measurements will be made in a space with a flat floor, with adequate beacons and accompaniment of the researchers in order to mitigate the risk of falls.

Complications of forced spirometry are rare. The most common are coughing fits, bronchospasm, chest pain, dizziness, urinary incontinence or increased intracranial pressure. Very rarely, the patient may experience syncopal symptoms. For this, the spirometry will be performed at the Hospital Universitario del Valle, by a professional trained and experienced in performing these, and in the event of any of these events, the test will be suspended and If the symptoms do not subside, the emergency service will be consulted directly. This test will be performed to rule out the coexistence of any alteration in lung function.

In general, there are very few risks or possible complications with the incentive spirometer, but it is important to stop if you feel dizzy. However, there are rare reports of pneumothorax that have been associated with very aggressive spirometry in people with emphysema (and pulmonary bullae that could rupture), in this case if the patient is uncomfortable the test will be discontinued, the other major risks were ruled out with the result of the spirometry in a normal state, in addition, the technique will be performed and guided by the researcher, who is a physiotherapist with experience in handling the technique and trained in case of any eventuality.

The IMP is a device for therapeutic use, which has an industrial design registration, granted by the Superintendence of Industry and Commerce to the Universidad del Valle under the name of "Inspirometro". So its use is supported.

This research was approved by the Human Ethics Committee of the Universidad del Valle under code 031-022 (Annex 1).

The selected subjects must be previously informed in a clear and concise manner by the researcher about the objective of the research, and the informed consent must be read and explained to the participant and to the person who will be a witness, for subsequent signature. A copy must be delivered to both. The information generated by this study will be strictly confidential; privacy will be maintained and the participant will not be identified in any publication.

To protect the data and security of the participant, the following will be considered:

- The person who will apply the measurements underwent training with the personnel of the commercial house that distributes the Pulmovista equipment (EIT) to certify the qualification in carrying out the measurements.
- The informed consent will be read to each of the people who participate in the study, each and every one of the benefits and risks to which they will be exposed will be explained.
- It will be explained that the information generated is strictly confidential and will be used for academic purposes, its privacy will be maintained and it will not be identified in any publication; all data will be identified with a 4-digit sequential code, which will end with the last 2 numbers of the current date
- The information will be stored digitally in the main investigator's computer, with absolute confidentiality and guaranteeing the use of a password to access it. Strict privacy will be kept regarding the records that may identify you; and it will be stored for 10 years, for future publications or for the development of subsequent projects if the participant so authorizes it.
- There is no conflict of interest in this study.

## Study Variables

The variables to be measured are:

### Main variables:

- EELI Delta ( $\Delta$ EELI): Measures the change in the average end-expiratory pulmonary impedance before and after an intervention.
- MTV ROI: Minute regional tidal variation

### Secondary variables:

- IPAQ: Instrument that provides information on estimated energy expenditure in 24 hours in the different areas of daily life.
- Charlson index: Relates long-term mortality with the participant's comorbidity
- %FEV1 pred: Percentage of the predicted forced expired volume in the first second
- %FVC pred: Percentage of predicted forced vital capacity
- %FVC/FEV1: Percentage of predicted of relationship between forced vital capacity and FEV1
- Labor Occupation: Includes the labor function of the worker
- Level of schooling: the highest level of studies completed or in progress
- Marital status: situation determined by your family relationships, from marriage or kinship
- Socioeconomic Stratum: Classification in strata of residential properties
- Personal history: Compilation of information on the health of the person and pathologies that he/she suffers from.

- Height: Measurement of the height of the human body from the feet to the roof of the cranial vault.
- Weight: Force with which bodies are attracted towards the center of the earth by the action of gravity
- BMI: Relationship between weight and height
- Heart rate: Number of times the heart contracts in one minute
- Respiratory rate: Number of breaths in one minute
- Oxygen Saturation: Measurement of the amount of oxygen available in the blood
- Dyspnea: Difficulty breathing

## Materials and Instruments

The instruments that will be used in the study will be: Height rod, scale, Spirometer, modified Pachon's incentive, Hudson Flow Respiratory Incentive, equipment to measure impedance (Pulmovista), data collection format. And they are described below:

- Modified Pachon's incentive (Incentivo Modificado de Pachon by the name in Spanish): handmade device that mimics conventional respiratory incentives, but is made with recyclable, low-cost materials and is also easy to manufacture. Modified in 2004 in a research work by students from the Universidad del Valle(10), where they analyzed the characteristics of the materials required for its design and carried out laboratory tests, they defined that the IMP allows mobilizing flows that oscillate between 600 cc/sec up to more than 1400 cc/sec which characterizes it as a flow incentive. The materials used for its construction are a non-lubricated buretrol and a Today brand condom, since other condoms that have lubricant present discomfort for handling, makes the condom adhere to the walls of the buretrol, and hinders its displacement.
- Triflo® II Respiratory Incentive: Method of encouraging deep voluntary breathing, which provides participants with visual feedback of inspiratory volume, by means of 3 color-coded balls in three chambers, with mouthpiece and tube. The minimum flow is marked on each chamber: 600, 900 and 1200 ml/Seg. It is used to help with inspiratory muscle training and prolonged maximal inspiration, deep breathing stimulates the alveoli to fully expand, it is also often used to prevent or reverse the formation of pulmonary atelectasis. It is manufactured by HUDSON RCI
- PulmoVista 500®: it is an electrical impedance tomograph, from Dräger. The data is continuously represented in the form of images, curves and parameters to observe ventilation continuously and directly in various lung regions, as well as the changes

that occur in lung volumes at the end of expiration, non-invasively, in time, real and directly next to the bed.

- Spirometer: This is a device that is commonly used to assess how well the lungs are working by measuring how much air you breathe in, how much you breathe out, and how quickly you breathe out. Spirometry is used to diagnose asthma, chronic obstructive pulmonary disease (COPD), and other diseases that affect breathing. Spirometry can also be used periodically to monitor the condition of your lungs and see if treating chronic lung disease is helping you breathe better. For this study, a medgraphics cardiorespiratory diagnostics® brand spirometer will be used, which works with the breeze suite 6.4.1.44 SP4 system.
- Stadiometer: it is a height meter that is fixed to the wall or to a support and is used to accurately measure people, so that when it is placed under it, the stadiometer will rest on their head, indicating the height on the dial. exactly who is using it. For this study, a SECA model 213® stadiometer will be used.
- Scale: Device used to measure weights. For this study, a SECA® brand scale will be used.

For this research, a data collection format was designed:

- Format created by the researcher made up of a section on sociodemographic information (age, date of birth, gender, sociodemographic stratum, occupation, education and marital status), personal and family history (the Charlson index will be applied to assess associated comorbidities, anthropometric data (weight and height), level of physical activity (IPAQ), lung function data (spirometry) and results on ventilation and global and regional lung impedance for each individual.

To measure clinical stability and the level of physical activity, the following instruments will be used:

- Charlson Index: it is a life expectancy evaluation system, depending on the age at which it is evaluated, and the subject's comorbidities. In addition to age, it consists of 19 pathology items with their respective rating, which, if present, have been found to have a specific influence on the subject's life expectancy. In general, absence of comorbidity is considered: 0-1 points, low comorbidity: 2 points and high > 3 points. The prediction of mortality under 3 years: score of 0: (12% mortality/year); from 1-2: (26% mortality/year); from 3-4: (52% mortality/year); and > 5: (85% mortality/year).
- International Physical Activity Questionnaire (IPAQ) short version IPAQ researchers developed several versions of the instrument according to the number of questions (short or long). The short version consists of 7 items and provides information about the time the person spends performing moderate and vigorous intensity activities, walking and sitting. Especially recommended when population monitoring is intended in research

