### **Phase 2: Design and Adjustment of Instruments**

The data collection instrument will be designed.

For the standardization of anthropometric measurements (weight and height), Standardized Operating Procedures 1 and 2 will be used according to the instructions defined in these

For the measurement of the EIT, the Standardized Operating Procedure 3 designed for projects previously carried out by GIESC will be used. "Effect of two lung reexpansion techniques on the ventilation of participants undergoing cardiovascular surgery. Controlled clinical trial phase II b"

The pilot test will be carried out with 5 healthy subjects who will not be part of the sample, they will be informed about the research, they will be asked to sign the informed consent and the measurements and data collection will be carried out with the designed data

collection format. by the researcher. Said pilot test will be carried out to test and make pertinent corrections in the management of the evaluation instruments and in order to identify the times required in the measurement of the variables.

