##### **Performing spirometry**

This measurement will be carried out at the Hospital Universitario del Valle, in the physical medicine and rehabilitation unit in the pulmonary function laboratory with the medgraphics cardiorespiratory diagnostics® brand spirometer that belongs to the Universidad del Valle and is under the custody of the Hospital Academic. The spirometries will be carried out by the researcher, who is a physiotherapist specializing in cardiopulmonary physiotherapy. The day of the test will begin with the completion of the informed consent, this will be read and explained to the participant and will continue to the signature. On this day, the researcher will fill out the sociodemographic data of the participant, weight and height measurement, Charlson index and IPAQ abbreviated questionnaire, according to the instructions defined in the Standardized Operational Procedures 1, 2, 4 and 5 for these procedures in the data collection format. data.

Spirometry will be performed according to the institutional protocol of the Hospital Universitario del Valle. The duration of this procedure will take approximately 1 hour

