### **Moments of electrical impedance tomography measurement**

Once the patient is connected to the tomograph, the quality of the signal must be checked. Once it is verified that it is being measured properly, that the patient is well positioned and that the signal is of high quality, the recording will begin. tomograph record; after the first

two minutes of calm breathing have elapsed, the first event will be marked, which will be recorded as "pre", and the use of the corresponding respiratory incentive will begin. The proper use of the device will be previously explained to you through a video that will illustrate the correct way to use it. The participant will receive visual feedback from the device when the condom is raised within the buretrol in the case of the IMP or when the spheres are raised in the branded incentive "Triflo II®"

Three series of ten breaths will be performed, with a 1-minute rest between series. In the last repetition of the third series, the second event will be marked, which will be recorded as "intra".

The maneuver will be finished once the series and repetitions are finished, removing the mouthpiece from the participant's mouth and they will be asked to continue breathing calmly for 2 minutes, after which the third event will be marked, which will be recorded as "post". And the recording of the record will be terminated.

At the beginning and at the end of the intervention, clinical data will be taken (heart rate, respiratory rate and oxygen saturation) and 15 minutes after finishing the test.

Taking into account that the subjects are using a device that is not used routinely in daily life, the perception of the subject in the use of each of the devices will be evaluated to know the degree of comfort of these by means of the scale of Likert and in the same way it will be valued if I generate perception of dyspnea by means of the Borg scale

The session may be interrupted if the participant does not wish to continue with the intervention, if the participant shows intolerance to the maneuver, if the respiratory rate is greater than 25 breaths per minute and if there is use of accessory muscles.

After each measurement is finished with each participant, the equipment will be disinfected

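### Every participant uses the handmade IMP, but no eligibility item excludes a volunteer with a known allergy to its materials

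*Combined protocol and SAP*

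**What the plan says.** Materials and Instruments describes the IMP as a handmade, low-cost device: "The materials used for its construction are a non-lubricated buretrol and a Today brand condom". It prefers this condom because lubricated ones are awkward to handle and stick to the chamber wall. It does not say what the condom is made of.

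Study Design puts the device in everyone's hands: "Both incentives will be used on all participants, and the order of assignment will be randomized". Population Sample sets the number at 18. The section on moments of EIT measurement describes the use: three series of ten breaths, a mouthpiece that is removed at the end, and "The participant will receive visual feedback from the device when the condom is raised within the buretrol in the case of the IMP".

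The inclusion criteria cover age, clinical stability, body mass index, mental and cognitive state, and consent. The exclusion criteria cover implanted cardiac devices, metal implants, poor signal, pregnancy, obstacles to fitting the electrode belt, high physical activity, abnormal spirometry, and failure to understand the instructions for the incentive.

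Personal history is listed among the secondary variables as "Compilation of information on the health of the person and pathologies that he/she suffers from". For the spirometry visit the protocol says: "On this day, the researcher will fill out the sociodemographic data of the participant, weight and height measurement, Charlson index and IPAQ abbreviated questionnaire". Phase 2 adds a pilot: "The pilot test will be carried out with 5 healthy subjects who will not be part of the sample".

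**The concern.** Eligibility criteria decide who is exposed to a study device. Here the device under test is assembled by hand from named components, and every participant breathes through it. A person who already knows that a component causes an allergic reaction is the easiest person to keep away from it, since one question is enough. The criteria contain no rule that does so.

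What is at stake is participant safety. There is a conditional consequence for the data: if a reaction ended an IMP session, that participant would have no complete pair for the paired t test, which is 1 of 18. No planned test or error rate is affected otherwise.

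**Working it through.** The plan states no figure on this point, so the check is a reading of the criteria against the exposure, with simple counts.

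1. **Exposure.** Study Design gives the IMP to all participants, and Population Sample plans 18. The measurement section gives 3 × 10 = 30 breaths per device session, so the IMP is used for 18 × 30 = 540 breaths in the main sample. This counts use of the device. It does not show contact with an allergen.

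2. **Pilot.** Phase 2 adds 5 people outside the sample and does not spell out which devices they use. If all of them use the IMP, at most 18 + 5 = 23 people do.

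3. **Criteria.** There are 5 inclusion items and 8 exclusion items, 13 in all. Items that concern allergy or hypersensitivity to a device material: 0 of 13.

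4. **Nearest inclusion item.** Clinical stability requires no acute illness in the previous 6 weeks and a Charlson score of 0-1. A person with a known material allergy and no other illness can meet both conditions.

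5. **Other places that could close the gap.**
   - Personal history is a secondary variable. An allergy may surface there, but no rule makes the person ineligible. The list of what is completed on the spirometry day does not name personal history either, so the visible text does not fix when it is taken.
   - The interruption grounds (the participant's wish, intolerance of the manoeuvre, respiratory rate above 25 per minute, use of accessory muscles) act only after use has begun.
   - The abandonment criterion is the participant's own request.

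None of these makes a volunteer with a known allergy ineligible before the device order is drawn.

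**The case against.** The strongest objection is that the hazard is not in the documents. The protocol names a brand of condom, not its material. It describes the condom moving inside the chamber and does not describe skin contact. The Triflo II mouthpiece, the spirometer and the electrode belt have no material-allergy exclusion either. This stands as a limit on how much weight the point can carry. It does not remove the point, which rests only on the missing rule for a device that all participants use.

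A second objection is that safeguards exist. The Ethical aspects section promises that all risks will be explained at consent. A video shows correct use of the device. An experienced physiotherapist guides the technique and stops if the participant is uncomfortable. A volunteer who knows of an allergy may speak up. Consent pages and operating procedures 6 and 7 are not visible and may contain a warning. All of this is fair and lowers the concern, but none of it is an eligibility rule.

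Three stronger readings are tempting and are not supported:

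- A reader might infer that the protocol screens for allergy to one piece of equipment and forgot the other, because it excludes "Participants with injuries, skin changes or presence of devices that prevent the placement of the electrode belt around the chest". That item is about whether the belt can be fitted. It is not an allergy screen.
- A reader might infer that the protocol claims spirometry rules out allergy, from "the other major risks were ruled out with the result of the spirometry in a normal state". Those words belong to a sentence about pneumothorax in people with emphysema.
- A reader might assume an allergy frequency and compute the chance that at least one of 18 is affected. The documents give no frequency to start from. The result would be the chance of enrolling someone with a known allergy, not the chance of a reaction.

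**Conclusion.** The point holds as a minor participant-safety improvement. Of 13 eligibility items, none concerns known allergy to the materials of a handmade device that all 18 participants use, so a volunteer who knows of such an allergy is eligible as written.

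The risk cannot be sized. The condom's material, the route of exposure and the frequency of allergy are all absent from the documents. A reader might infer that the condom is latex, or that participants are exposed to a demonstrated allergen; the text establishes neither. The conclusion assumes that the visible inclusion and exclusion lists are complete, and it says nothing about what the consent form or the operating procedures contain.

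The sample size, the paired comparison and its error rate stay as planned.

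**What to change.** - Add one exclusion: known allergy to any IMP material (buretrol, condom, mouthpiece).
- Ask the question at the spirometry visit, after consent and alongside the Charlson and IPAQ questionnaires, so that it is settled before randomization.
- State the condom's material under Materials and Instruments, so that the volunteer can answer.
- Ask the 5 pilot subjects the same question if they use the IMP.

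The cost is one question at a visit already planned, one line in the criteria, and notice of the change to the ethics committee. The downside is that an occasional volunteer will be turned away and must be replaced in the same age-sex cell, each of which holds 3 people.
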